4 RESEARCH QUESTION/AIM(S)

4.1 Objectives

The BRITER study is being performed in patients aged 65 or over who have a new diagnosis of GBM. It tests the hypothesis that there is a relationship between 5 scores of a 'vulnerable' brain seen on pre-treatment MRI and a clinically significant change in patient quality of life, as defined by a 10 point change in the EORTC QLQ questionnaire from baseline to 8 weeks post treatment.

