4.2 Outcome

The primary outcome is the proportion of patients with a 10 point change in the EORTC QLQ C30 quality of life questionnaire (with the BN-20 brain and ELD14 elderly patient subsets of questions added) from baseline to 8 weeks.

The impact of side effects from cranial radiotherapy will also be assessed by the secondary outcomes of

- MOCA cognitive screening questionnaire
- use of corticosteroids
- degree of grade 3-5 CTCAE toxicity
- overall and progression free survival

5 STUDY DESIGN and METHODS of DATA COLLECTION AND DATA ANALYSIS

The BRITER study is an observational cohort study. Eligible patients will be identified during the multidisciplinary team meeting by the participants' usual care team. They will have previously been informed of their diagnosis and then will meet a member of the oncology team to discuss treatment options. Once it has been decided with them by their usual care team that they are to have radiotherapy treatment, they will be given a PIS. After the patient has had sufficient time to read the PIS and have any questions answered by a member of the study team they will be asked to complete a consent form. They will also undergo the baseline clinical assessments prior to starting any

radiotherapy treatment. This will be done during the outpatient appointment with the neuro oncology team.

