The participant's treatment plan is not affected by enrolment in the study. The participant will then complete their radiotherapy treatment as planned. When they attend for their routine 4 week post-treatment follow up to the NHS neuro-oncology clinic they will repeat the EORTC-QLQ-C30 quality of life questionnaires and MOCA questionnaire as well as having assessment of their CTCAE radiotherapy toxicity score and steroid use. Again the EORTC-QLQ-C30 quality of life questionnaires could be sent to the patient in advance to complete prior to the clinic appointment or taken home and posted back. If the patient is unable to come to a clinic appointment during the required time frame they can be posted a questionnaire and send it back. The questionnaires should be completed within 3 to 5 weeks after treatment has finished. These will be recorded in the CRFs. Members of the study team are permitted to phone the patient to remind them to complete the questionnaires if they are not returned or can complete them over the phone with the patient. This would normally be done by the CNS or doctor who the patient will already know as part of their usual care team and would be accustomed to speaking to on the phone.

When participants attend for their routine 8 week (plus or minus 1 week) post-treatment follow up to the NHS neuro-oncology clinic they will repeat the same questionnaires and toxicity assessment. At this point their participation in the study is complete.

At the end of the study the results of the questionnaires from the CRFs will be transcribed into a database using Microsoft Excel. The CRFs will not contain the patient's name or recognisable patient details and the database will therefore be pseudo anonymised. A score of 24 or less on MOCA will be deemed abnormal. A change in baseline of 10 points or more on the EORTC-QLQ-C30 quality of life questionnaires will be deemed significant.

The MRI scans for the participants will be anonymised using the patient study ID and electronically transferred to [name], neuroradiologist The Walton Centre in Liverpool, for analysis. The following MRI sequences are ideally required:

- Axial T2 4mm slice thickness
- Volumetric T1 pre contrast (1mm or below)
- Post contrast volumetric T1 (1mm or below)
- DWI/ADC (4 mm slice thickness)
- Susceptibility weighted imaging (acquired volumetrically typically in the region of 1.5mm slice thickness but will vary with scanner setup)

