- 3D volumetric inversion recovery or MP-RAGE (additional sequence - to allow accurate quantification of cortical thickness/volumes using Freesurfer software in addition to scoring methods of atrophy, must be acquired at 1mm or below)
- Axial T2* gradient echo (4mm slice thickness)

The scan thickness and sequences performed may vary slightly between sites however prior to opening the sites will confirm they can produce the necessary sequences for [name] to produce 5 quantitative scores (tumour volume, contralateral hemispheric brain volume, contralateral cerebral hemisphere cortical thickness, microhaemorrhage score and white matter hyperintensity score) from the images which reflect the degree of potential vulnerability of the brain to the side effects of radiotherapy. These will then be analysed in relation to the clinical questionnaires, steroid usage and grade 3-5 CTCAE radiotherapy toxicity score using SPSS. Multivariable logistic regression models will be fitted to look for significant ($P<0.05$) relationships between the 10 point change in EORTC QLQ quality of life questionnaires and the MRI parameters. Exploratory statistical analysis of the relationships between the MRI parameters and the secondary endpoints will be performed although the study is not powered to detect statistically significant relationships between these.

The creation of the database and statistical analysis of the results will be performed by the CI with the help of a research assistant.

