7.2 Sampling

7.2.1 Size of sample

Sample size calculations have been performed assuming a clinically significant end point of a 10 point change (SD=22.1 taken from the EORTC website reference guide) in EORTC QLQ questionnaire score between baseline and 8 weeks. Estimated sample size for one-sample comparison of proportion to hypothesized value assuming a 2 sided alpha of 0.05 and power of 0.9 gives a sample of

73. However, allowing for 20% attrition in questionnaire completion, this results in a sample size of 91. With 73 patients at 8 weeks, we will have 90% power for 5% significance to detect 5% of patients achieving a 10 point change in QoL. However, this small a proportion will only allow us to fit one variable in the model. It has therefore been recommended by the statistical team to aim for a recruitment target of 100 patients in order to fit the 5 MRI variables to the model.

Patients who are enrolled within CTIMP studies will not be eligible to be recruited into the study as they would introduce too many unknown variables for adequate statistical analysis with a cohort of this size.

Previous work done by this study group has shown this is a feasible recruitment target over 2 years.

The study team will review recruitment at 9 months and if it has not reached 25% then they will explore ways to increase recruitment, including opening at other sites.

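### The link between MRI scores and quality of life is tested only through a 10-point yes/no outcome with no baseline score; a baseline-adjusted continuous analysis of the same data would be a stronger main test

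*Combined protocol and SAP*

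**What the plan says.** - **Hypothesis (section 4.1).** Five MRI scores are related to a clinically significant change in quality of life, "as defined by a 10 point change in the EORTC QLQ questionnaire from baseline to 8 weeks post treatment".
- **Primary outcome (section 4.2).** "The primary outcome is the proportion of patients with a 10 point change in the EORTC QLQ C30 quality of life questionnaire", with the brain and elderly modules added. No single scale or summary score is named, and the direction of change is not given.
- **Cut-point (section 5).** "A change in baseline of 10 points or more on the EORTC-QLQ-C30 quality of life questionnaires will be deemed significant".
- **Model (section 5).** "Multivariable logistic regression models will be fitted to look for significant" relationships at P<0.05 between the 10-point change and the MRI parameters. No baseline quality-of-life term and no continuous quality-of-life model is described. Section 2, however, speaks of assessing the MRI scores for correlation with changes in quality of life.
- **Sample size (section 7.2.1).** The calculation is a "one-sample comparison of proportion to hypothesized value assuming a 2 sided alpha of 0.05 and power of 0.9", giving 73 patients, or 91 after 20% attrition. The text adds that "we will have 90% power for 5% significance to detect 5% of patients achieving a 10 point change in QoL" but that "this small a proportion will only allow us to fit one variable in the model". It then raises the target to 100 so that five MRI variables can be fitted.

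**The concern.** The same questionnaire is completed at baseline and at 8 weeks, so a score is available at both times. The plan reduces the pair to one yes/no value. A patient who changes by 9 points is then treated as unchanged, and one who changes by 11 is treated the same as one who changes by 40.

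Two losses follow. The first is the information in the size of the change. The second is the precision that the baseline score would add as a covariate. Without that covariate, regression to the mean also influences who crosses the cut, because patients with extreme baseline scores are more likely to move.

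The number of predictors a logistic model can carry depends on the number of events, and the plan itself worries about this. A linear model does not have that constraint: 80 completers, an intercept, five MRI scores and the baseline score leave 80 - 7 = 73 residual degrees of freedom.

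The risk is a false negative. Section 3 hopes to identify patients for whom radiotherapy may be a poor choice, and a missed relationship would end that line of work. No power is stated for the model that tests the hypothesis.

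**Working it through.** **1. The plan's own figure.** One-sample proportion, normal approximation: n = [z(0.975)·√(p0·q0) + z(0.90)·√(p1·q1)]² / (p1 - p0)². With p0 = 0.05 and p1 = 0, n = 1.960² × 0.0475 / 0.0025 = 72.99, so 73 is reproduced. Then 73/0.8 = 91.25, against 91 stated. Two things follow:
- The 5% enters as the null proportion, so it is not clearly an expected responder rate, although the text goes on to call it small and to limit the model by it.
- The quoted "SD=22.1 taken from the EORTC website reference guide" does not enter. A one-sample mean with a difference of 10 would give (1.960 + 1.282)² × 22.1² / 10² = 51.3, so 52.

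Neither calculation is about the logistic model.

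**2. Events.** 100 recruited less 20% leaves 80 completers.
- At 5%: 80 × 0.05 = 4 events for five predictors.
- At 32.5%: 80 × 0.325 = 26 events, about 5 per predictor.

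**3. Information kept by the cut.** For a normal outcome cut in one direction, relative efficiency = φ(z_p)² / [p(1 - p)].
- If 22.1 is the SD of change and the mean change is 0, p = 1 - Φ(10/22.1) = 0.325. Efficiency is 0.59, a loss of 41%.
- At p = 0.05, efficiency is 0.22, a loss of 78%.
- The smallest possible loss, at p = 0.50, is 36%.

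The first two are different worlds. With SD 22.1, a 5% rate puts the cut 1.645 × 22.1 = 36.35 points from the mean. The mean would therefore have to lie about 26 points further from the cut than in the first scenario. If 22.1 is the SD of a score, with baseline-to-8-week correlation 0.3-0.7 and mean change 0, the loss is 40-44%.

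**4. The dichotomy alone, in closed form.** Take one marker correlated 0.3 with change, n = 80 and no baseline term in either model. The noncentrality is √80 × 0.3/√0.91 = 2.81.
- Continuous: Φ(2.81 - 1.96) = 0.80.
- Cut at 32.5%: Φ(2.81 × √0.591 - 1.96) = 0.58.
- Cut at 5%: Φ(2.81 × √0.224 - 1.96) = 0.26.

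**5. Joint test of five scores, simulated.** Settings, all assumed: 80 completers, SD of change 22.1, correlation 0.5, five independent scores with equal effects, 5% level. The F test is used for linear models and the likelihood-ratio test for logistic models. Residual variance after baseline is 22.1² × 0.75 = 366. Scores explaining 15% of it correspond to √(0.15 × 366) = 7.4 points per SD of the combined score; 10% and 35% correspond to 6.1 and 11.3 points.

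| Analysis | Power at 15% explained | Power at 10-35% explained |
|---|---|---|
| Linear, 8-week score adjusted for baseline | 0.80 | 0.55-1.00 |
| Linear on change, no baseline | 0.65 | not tabulated |
| Logistic with baseline, 32.5% events | 0.49 | not tabulated |
| Logistic as planned, 32.5% events | 0.43 | 0.29-0.87 |
| Logistic as planned, 5% events | 0.16 | 0.16-0.36 |

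Repeat runs at 15% gave 0.78-0.80, 0.43-0.45 and 0.16-0.20 for the first, fourth and fifth rows. At 5% events some 7-13% of fits failed, depending on the failure criterion, so that row is the least firm.

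**6. Splitting the gap at 15% and 32.5% events.** The total is 0.80 - 0.43 = 0.37. Leaving out baseline accounts for 0.80 - 0.65 = 0.15, and the dichotomy for 0.65 - 0.43 = 0.22. Taken in the other order, adding baseline to the logistic model recovers 0.49 - 0.43 = 0.06, and the dichotomy costs 0.80 - 0.49 = 0.31.

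**7. Sensitivity.** With one active marker at 5-9 points per SD and correlation 0.3-0.7, the ratio of logistic (Wald) to baseline-adjusted linear power is 0.53-0.81 at 32.5% events, 0.43-0.73 at 20% and 0.13-0.29 at 5%.

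**The case against.** **A responder outcome is a legitimate target.** The cut is prespecified and described as clinically significant, and section 3 wants to know which patients are vulnerable. Points per unit of MRI score answers a somewhat different question. This stands: the plan is not in error for having such an outcome, and the outcome should be kept. It does not follow that the responder outcome must also be the only test of whether a relationship exists.

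**The power loss is not fixed by the documents.** They give no MRI effect size, no baseline-to-8-week correlation, no mean change and no responder rate beyond the 5%. A reader might infer that the dichotomy as such halves power. The documents do not support that. At 32.5% events and correlation 0.5, the power ratio runs from 0.52 to 0.87 as explained variance goes from 10% to 35%. Part of the gap comes from the missing baseline term, which could be added to the logistic model.

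**41% and 78% are not one range for this trial.** They belong to incompatible scenarios, and the 78% rests on a proportion that the sample-size formula uses as its null value. This also stands. If change in either direction counts, the single-cut formula does not apply.

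**The plan has answered the one-variable limit by recruiting 100.** The limit is tied to 73 patients and a 5% proportion. At 5% the response is inadequate: the expected events go from 73 × 0.05 = 3.65 to 4. At 32.5% the position is much better.

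**Conclusion.** The concern holds as an avoidable inefficiency. The plan tests its hypothesis only through a 10-point yes/no outcome in a five-predictor logistic model without the baseline score, although the data for a stronger test are collected.

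Under normality and a one-directional cut, at least 36% of the information is lost wherever the cut falls. The loss is about 41% if 32.5% of patients cross it and about 78% at 5%. The power cost ranges from modest to severe according to effect size and event rate. In the central case (80 completers, correlation 0.5, 15% explained variance, 32.5% events) power is 0.43 against 0.80, with both the dichotomy and the missing baseline term contributing. At 5% events the five-predictor model is not workable.

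The direction and comparative size of the loss are secure under the normal linear model; the exact power figures rest on assumed values. The stronger conclusions that a reader might draw, that the responder outcome is invalid or that power is halved whatever the truth, are not supported.

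**What to change.** 1. Name one EORTC scale or summary score for the primary analysis. Without it, neither the linear nor the logistic model is defined.
2. Make the main test of the relationship a joint test of the five MRI scores in a linear regression of the 8-week score on that scale, adjusted for its baseline score.
3. Keep the proportion with a 10-point change as the clinical summary, and state the direction that counts.
4. Keep the logistic model as supporting, also adjusted for the baseline score. State in advance what will be done if there are too few events to fit five scores.
5. Align the objective (section 4.1), the outcome (section 4.2) and the sample-size text (section 7.2.1). The last should give power for the joint test with the assumed explained variance and correlation.

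**Cost.** No new data, visits or patients. The main effect is reported in points per unit of MRI score instead of as an odds ratio, which is less direct for treatment discussions; the retained 10-point summary offsets this. The change reaches the objective and outcome wording as well as the analysis section. If the sponsor prefers to keep the responder outcome as the main test, the least change is to justify the dichotomy, add the baseline score to the logistic model, and prespecify the linear model as a secondary analysis.

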4.2 Outcome

The primary outcome is the proportion of patients with a 10 point change in the EORTC QLQ C30 quality of life questionnaire (with the BN-20 brain and ELD14 elderly patient subsets of questions added) from baseline to 8 weeks.

The impact of side effects from cranial radiotherapy will also be assessed by the secondary outcomes of

- MOCA cognitive screening questionnaire
- use of corticosteroids
- degree of grade 3-5 CTCAE toxicity
- overall and progression free survival

5 STUDY DESIGN and METHODS of DATA COLLECTION AND DATA ANALYSIS

The BRITER study is an observational cohort study. Eligible patients will be identified during the multidisciplinary team meeting by the participants' usual care team. They will have previously been informed of their diagnosis and then will meet a member of the oncology team to discuss treatment options. Once it has been decided with them by their usual care team that they are to have radiotherapy treatment, they will be given a PIS. After the patient has had sufficient time to read the PIS and have any questions answered by a member of the study team they will be asked to complete a consent form. They will also undergo the baseline clinical assessments prior to starting any

radiotherapy treatment. This will be done during the outpatient appointment with the neuro oncology team.

Baseline clinical assessment of the patients will be conducted in the NHS neuro-oncology outpatient clinic setting. These will involve the EORTC-QLQ-C30 quality of life questionnaire with the BN-20 brain and ELD14 elderly patient subsets of questions added, the MOCA questionnaire (please see Appendix for examples of these questionnaires) and a record of the amount of corticosteroid the patient is currently taking. The EORTC-QLQ-C30 quality of life questionnaires are designed to be completed by the patient (they are allowed to ask for help completing from family/carer) and could therefore be taken home by the patient or completed in the waiting room rather than being completed within the clinic. There is a risk of the questionnaires not being filled in and posted back if participants forget. We have costed for stamped addressed envelopes to be given to the patients in order to post the questionnaires back. The study team (who know the participant and would usually speak to them on the phone anyway during their treatment pathway) are able to call the participant to remind them to post back the questionnaires. The MOCA is administered by a member of the study team.

The original copies of these questionnaires will be in the CRF, alongside details of the participant's age, gender, comorbidities, treatment plan and social situation which will be recorded by the study team.

In most cases, the participant will have undergone an MRI scan as part of their usual care plan prior to attending the neuro-oncology clinic. If this scan has the required imaging sequences needed for the BRITER protocol then no further scanning is required. This will be assessed by the neuro oncology consultant during the outpatient clinic appointment or a member of the study team prior to the appointment. A list of the required sequences will be readily available for the study team during this process. If not all of the required sequences were completed then the patient will undergo a further MRI scan. This will be done prior to the participant starting radiotherapy treatment but should not delay the start of their radiotherapy treatment. Depending on local guidelines, this scan will either take place on the same site or may require travel to another site. Travel costs will be covered for the patient and carer to attend the extra MRI scan.

The participant's treatment plan is not affected by enrolment in the study. The participant will then complete their radiotherapy treatment as planned. When they attend for their routine 4 week post-treatment follow up to the NHS neuro-oncology clinic they will repeat the EORTC-QLQ-C30 quality of life questionnaires and MOCA questionnaire as well as having assessment of their CTCAE radiotherapy toxicity score and steroid use. Again the EORTC-QLQ-C30 quality of life questionnaires could be sent to the patient in advance to complete prior to the clinic appointment or taken home and posted back. If the patient is unable to come to a clinic appointment during the required time frame they can be posted a questionnaire and send it back. The questionnaires should be completed within 3 to 5 weeks after treatment has finished. These will be recorded in the CRFs. Members of the study team are permitted to phone the patient to remind them to complete the questionnaires if they are not returned or can complete them over the phone with the patient. This would normally be done by the CNS or doctor who the patient will already know as part of their usual care team and would be accustomed to speaking to on the phone.

When participants attend for their routine 8 week (plus or minus 1 week) post-treatment follow up to the NHS neuro-oncology clinic they will repeat the same questionnaires and toxicity assessment. At this point their participation in the study is complete.

At the end of the study the results of the questionnaires from the CRFs will be transcribed into a database using Microsoft Excel. The CRFs will not contain the patient's name or recognisable patient details and the database will therefore be pseudo anonymised. A score of 24 or less on MOCA will be deemed abnormal. A change in baseline of 10 points or more on the EORTC-QLQ-C30 quality of life questionnaires will be deemed significant.

The MRI scans for the participants will be anonymised using the patient study ID and electronically transferred to [name], neuroradiologist The Walton Centre in Liverpool, for analysis. The following MRI sequences are ideally required:

- Axial T2 4mm slice thickness
- Volumetric T1 pre contrast (1mm or below)
- Post contrast volumetric T1 (1mm or below)
- DWI/ADC (4 mm slice thickness)
- Susceptibility weighted imaging (acquired volumetrically typically in the region of 1.5mm slice thickness but will vary with scanner setup)
- 3D volumetric inversion recovery or MP-RAGE (additional sequence - to allow accurate quantification of cortical thickness/volumes using Freesurfer software in addition to scoring methods of atrophy, must be acquired at 1mm or below)
- Axial T2* gradient echo (4mm slice thickness)

The scan thickness and sequences performed may vary slightly between sites however prior to opening the sites will confirm they can produce the necessary sequences for [name] to produce 5 quantitative scores (tumour volume, contralateral hemispheric brain volume, contralateral cerebral hemisphere cortical thickness, microhaemorrhage score and white matter hyperintensity score) from the images which reflect the degree of potential vulnerability of the brain to the side effects of radiotherapy. These will then be analysed in relation to the clinical questionnaires, steroid usage and grade 3-5 CTCAE radiotherapy toxicity score using SPSS. Multivariable logistic regression models will be fitted to look for significant ($P<0.05$) relationships between the 10 point change in EORTC QLQ quality of life questionnaires and the MRI parameters. Exploratory statistical analysis of the relationships between the MRI parameters and the secondary endpoints will be performed although the study is not powered to detect statistically significant relationships between these.

The creation of the database and statistical analysis of the results will be performed by the CI with the help of a research assistant.

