The majority of GBM patients over 65 who are actively treated by oncologists receive some form of radiotherapy to the brain. Short term side effects from radiotherapy include fatigue, headache, cognitive defects, nausea, weakness and a need for increased steroid doses. Longer term side effects include persistent cognitive defects, long term fatigue and hormonal imbalances^{ix}. Radiation causes an inflammatory response within the brain tissue as well as disrupting the blood brain barrier. It affects the vasculature of the brain with endothelial cell damage leading to microvascular dilatation, thickening of the vessel wall and increased risk of microbleeds and ischemic strokes in the months to follow^x. There is a risk of inducing tissue necrosis from occlusion of small blood vessels within the brain parenchyma, leading to coagulation, focal necrosis and demyelination. Animal models have suggested radiation is cytotoxic to developing neuroglial progenitor cells with areas of stem cells such as the hippocampus and periventricular zones, particularly vulnerable to damage, leading to longer term neurocognitive decline^{xixii}. There is evidence to suggest that radiotherapy can stabilise or improve functional ability for some older patients with GBM aswell as providing a survival advantage however

clinical experience shows that the degree of side effects experienced and their impact on quality of life varies widely within this patient cohort.

Risk factors for toxicities from radiotherapy include dose, fractionation and age however we have no more accurate ways of predicting which patients are more likely to suffer side effects. MRI has been shown to accurately pick up microhaemorrhages and other ischemic changes which may correlate with a 'vulnerable' brain pre-treatment^{xiiixiv}. These MRI changes have been examined in Alzheimer and dementia research with correlations shown between MRI markers and disease severity^{xv}, however they have not yet been used within the neuro oncology setting.

We aim to examine the relationship between MRI markers of a 'vulnerable' brain and degree of acute side effects and change in quality of life amongst a population of older patients being treated with cranial radiotherapy for GBM.

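### The corticosteroid outcome has no metric, visit or baseline reference, so steroid use that predates radiotherapy can be mixed with radiotherapy effect; define it as dose at 4 and 8 weeks, adjusted for baseline dose.

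*Combined protocol and SAP*

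**What the plan says.** Section 4.2 introduces the secondary outcomes with the words "The impact of side effects from cranial radiotherapy will also be assessed by the secondary outcomes of" and includes among them "use of corticosteroids". Section 1 (Background) lists the short-term effects of radiotherapy, among them "nausea, weakness and a need for increased steroid doses".

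Section 5 covers measurement and analysis:

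- **Baseline:** "a record of the amount of corticosteroid the patient is currently taking".
- **4 weeks after treatment:** patients repeat the questionnaires "as well as having assessment of their CTCAE radiotherapy toxicity score and steroid use".
- **8 weeks after treatment:** "they will repeat the same questionnaires and toxicity assessment". Steroids are not named.
- **Analysis of the MRI scores:** "These will then be analysed in relation to the clinical questionnaires, steroid usage and grade 3-5 CTCAE radiotherapy toxicity score using SPSS".

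Section 5 also calls the analyses of MRI parameters against secondary endpoints exploratory and says the study is not powered for them. The primary outcome, by contrast, is explicitly a change; section 4.1 gives it "as defined by a 10 point change in the EORTC QLQ questionnaire from baseline to 8 weeks post treatment".

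**The concern.** The side effect in the Background is an increase. The outcome in 4.2 and section 5 is use, with nothing to say whether that means any use, a dose, a change in dose or a new start, or at which visit. The plan records the amount before radiotherapy, so it expects some patients to be on steroids already, and that use cannot be a radiotherapy effect. No stated analysis draws on the baseline amount.

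This matters because tumour volume is one of the five MRI scores. If patients with larger tumours tend to start on more steroid, and dose persists over time, volume will be associated with steroid use after treatment even if radiotherapy changed nothing. Section 3 says the aim is to identify patients who might be better served by other options, and a spurious volume signal could be taken as support for that. An undefined metric also leaves the choice open until the data have been seen.

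**Working it through.** **1. No plan figure to reproduce.** The documents give no effect size, SD, event rate or sample size for the steroid outcome. The sample size in 7.2.1 concerns quality of life.

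**2. Steroid mentions side by side.**

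| Place | What is fixed | What is not |
|---|---|---|
| Section 1 | The side effect is an increase | – |
| Section 4.2 | Name of the outcome | Metric, visit, baseline reference |
| Section 5, baseline | Amount recorded | Its role in any analysis |
| Section 5, 4 weeks | Steroid use assessed | Whether as an amount |
| Section 5, 8 weeks | – | Steroids not named |
| Section 5, analysis | Usage related to MRI scores | Change or baseline covariate |

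**3. Size of the possible artefact.** Let V be tumour volume, B baseline dose and F follow-up dose, all standardised. Assume corr(V,B) = ρ and corr(B,F) = r, and that V affects F only through B, so there is no radiotherapy-related volume effect. Neither ρ nor r is in the documents; both are assumptions.

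Then corr(V,F) = ρ × r. The chance of a two-sided 5% result is approximately P(Z > 1.96 − m) + P(Z < −1.96 − m), with m = atanh(ρr) × √(n − 3).

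Take n = 80, that is 100 recruited less the plan's 20% attrition, so √77 = 8.775:

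- ρ = 0.2, r = 0.4: ρr = 0.08, m = 0.0802 × 8.775 = 0.70, chance about 11%.
- ρ = 0.3, r = 0.5: ρr = 0.15, m = 0.1511 × 8.775 = 1.33, chance about 26%.
- ρ = 0.5, r = 0.7: ρr = 0.35, m = 0.3654 × 8.775 = 3.21, chance about 89%.

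Simulation at n = 80 (4,000 runs per setting) gave 11%, 27% and 90% for raw follow-up dose, and about 5% throughout once baseline dose was a covariate.

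**4. Which use of baseline works.** A separate simulation at n = 73, the plan's evaluable number at 8 weeks, used 2,000 runs per setting with r from 0.4 to 0.8. It gave these shares of significant volume–steroid associations with no true effect:

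| ρ | Raw follow-up dose | Simple change F − B | F adjusted for B |
|---|---|---|---|
| 0 | about 5% | about 5% | about 5% |
| 0.2 | 11–29% | 8–16% | 4–6% |
| 0.3 | 17–53% | 14–29% | about 5% |
| 0.5 | 40–95% | 29–67% | 5–6% |

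The simple change score fails because of regression to the mean. Under this model corr(V, F − B) = −ρ√((1 − r)/2). At ρ = 0.5 and r = 0.4 this is −0.5 × √0.3 = −0.27, and m in absolute value is 0.281 × √70 = 2.35. That gives about 65%, in line with the simulated 67%. The sign is negative, so larger tumours would appear protective.

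An unadjusted proportion with any increase has the same weakness. At n = 80 with normally distributed doses, volume was significantly associated with it in 12–43% of runs. If about half the doses are floored at zero (also an assumption), this falls to about 5–9%.

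**The case against.** The strongest reply is that 4.2 is only a list of names. Use and usage label a domain, and MOCA is listed there without mention of change too. Because the baseline amount is recorded, a change or baseline-adjusted analysis remains open. This stands as far as it goes. A reader might infer that the plan scores raw post-treatment use as a rule, but no section says so. The supportable statement is that the metric is undefined and that a raw-use analysis is what the wording most directly permits. The plan does write change explicitly for quality of life, so its absence here is not mere shorthand.

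Second, the mechanism rests on premises outside the documents. Nothing says that volume tracks steroid dose, and patients may enter after debulking surgery (7.1.1), so the relation between scan volume and baseline dose is unknown. This also stands: the range of 11% to 90% shows what is possible, not what will happen.

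Third, these analyses are exploratory and unpowered. That limits the consequence, but low power does not excuse an outcome that may measure something other than the named side effect, and the remedy is cheap.

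A reader might also infer that steroid increases mask quality-of-life declines and so undermine the primary outcome. The documents do not support that. Section 4.1 asks about change in quality of life, and section 5 says enrolment does not alter treatment. A patient whose quality of life holds under usual care is correctly coded for that question.

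**Conclusion.** The point holds in limited form. The steroid outcome lacks a metric, a visit and a baseline reference, although the side effect is described as an increase and the baseline amount is collected. Analysed as worded, it would combine pre-treatment need with radiotherapy effect. If tumour volume correlates 0.2 to 0.5 with baseline dose and baseline dose 0.4 to 0.7 with follow-up dose, about 11% to 90% of studies with no radiotherapy effect would show a significant volume–steroid association, against about 5% after baseline adjustment. If volume and baseline dose are unrelated, there is no inflation.

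This is more than a request for detail, because the choice of method matters: adjusted follow-up dose performs better than both raw use and a simple change score. The consequence is confined to an exploratory secondary analysis, and the primary outcome is unaffected. It should be corrected before analysis but does not threaten the study's main question.

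**What to change.** In 4.2 and section 5:

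1. Define the outcome as total daily corticosteroid dose, on one common equivalent scale, at 4 and 8 weeks after treatment.
2. Analyse it against the MRI scores with baseline dose as a covariate.
3. If the proportion with any increase over baseline is also reported, adjust that for baseline dose as well.
4. State that the steroid amount is recorded at both follow-up visits, since section 5 names steroid use only at 4 weeks and does not say there that it is an amount.

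The cost is protocol wording, one recorded item at 8 weeks and a unit conversion. The limit is that baseline adjustment does not separate radiotherapy effect from tumour progression after treatment, so results should be reported as exploratory. The primary outcome and steroid prescribing stay as they are.
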